Nicotine administration: Nicotine bitartrate will be obtained from Interchem Corporation, Paramus, NJ, and solutions for IV injection will be prepared by U.S. Specialty Formulations, Bethlehem, PA. On the morning of each test session, weight-adjusted nicotine and saline solutions will be prepared by the West Haven VA research pharmacy. Nicotine and saline will be administered using an infusion pump connected to an IV catheter located in a forearm vein. We have followed these procedures in our previous studies, which were completed without any serious adverse effects attributed to nicotine or other safety concerns. [name] holds an ITP (Investigational Tobacco Product) for IV nicotine administration. A new ITP application has been submitted to the FDA for this project.

In each test session, there will be a total of 3 infusions. Each infusion duration will be 10 minutes long, which will be achieved by infusing saline for the remainder of the time following the 2.5- and 5-minute nicotine infusions. A research nurse, will program 2 infusion pumps to administer nicotine or saline solutions. For the 2.5 and 5 min infusion conditions, participants will first receive nicotine for 2.5 and 5 minutes, followed by saline infusions. For the saline condition, participants will receive saline for 10 minutes. The participants will be blind to the randomization. The order of infusions will be: 1) 5-min or 2.5-min nicotine infusion, 2) saline infusion and 5-min or 2.5-min infusion. This infusion order was chosen to minimize carry over effects between nicotine infusions. Participants will be blind to the order of nicotine infusions.

Justification for the nicotine doses and infusion rates: The total nicotine dose for each test session will be 2 mg/70 kg body weight, a dose within the range of nicotine delivered by smoking 1 or 2 tobacco cigarettes or e-cigarettes (21). For safety reasons, the maximum dose of nicotine for each infusion will be 1 mg. The infusion rates will be 0.096 and 0.048 $\mu\text{g}/\text{kg}/\text{second}$ over 2.5 and 5 minutes, respectively.

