Medical monitoring: Participants will be given a thorough physical examination prior to study entry. For nicotine administration sessions, participants will be attached to a cardiac monitor as well as a blood pressure and heart rate monitoring device. An IV catheter for nicotine delivery will be in place throughout each test session. Participants will be administered nicotine only if the systolic blood pressure is <150 mmHg and heart rate is <90 beats/minute. Participants will be terminated from the study if the blood pressure at any time is >170/110 mm Hg, if the heart rate is >130 beats/min, or if they develop signs and symptoms consistent with nicotine toxicity. We have not encountered any cases of nicotine toxicity in our nicotine infusion studies. These study procedures were developed as part of our Investigational Tobacco Product (ITP) application to the FDA for IV nicotine.

Overview of the study: We propose a placebo-controlled study that will recruit male and female menthol nicotine dependent smokers. Following screening and evaluation as described above, eligible participants will be enrolled in the study which will last about 4 weeks. Eligible, participants will be randomized to menthol or non-menthol smoking condition for 2 weeks (Phase 1) and then will be switched to the alternative condition for another 2 weeks (Phase 2). The smoking condition will be open label. Participants will be provided with free cigarettes in Phases 1 and 2. For the menthol condition, participants will be provided their usual brand of menthol cigarettes and for the non-menthol condition, they will be provided a matched-brand non-menthol cigarette (e.g., Newport Non-Menthol Gold 100s for those who smoke Newport Menthol Gold 100s). In week 2 of each Phase, participants will have a test session. Each session will include 3 infusions in the following order: nicotine (1 mg per 70 kg body weight to a maximum dose of 1 mg) delivered over 2.5 or 5 minutes, saline delivered over 10 minutes, and nicotine (1 mg/ 70kg to a maximum dose of 1 mg) delivered over 2.5 or 5 minutes). For safety reasons, the maximum dose of nicotine for each infusion will be 1 mg. The infusion rates will be 0.096 and 0.048 µg/kg/second over 2.5 and 5 minutes, respectively. Once the participants complete the test session, participants will be crossed over to the alternative treatment. The period between the 2 Phases will not be longer than one week.

Table 1: Study Overview

Procedures	Study Phases	

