Test Session: The schedule of events during the test sessions is shown in Table 2. The sessions will begin around 8 AM, following overnight nicotine abstinence. Before the session begins, participants will have two indwelling catheters placed in antecubital veins, one for administering infusions and one for collecting blood samples. A blood sample will be drawn prior to the first infusion to measure baseline levels of plasma nicotine and menthol glucuronide and for women, additional samples for the measurement of estradiol and progesterone levels will be collected. Baseline measurements will then be collected including heart rate, blood pressure, self-report assessments and cognitive testing. Participants will then receive the assigned infusion over a period of ten minutes. Psychometric assessments and blood sampling will then continue for the next 120 minutes. Participants will be discharged after evaluation by the study physician. Participants will also receive their assigned cigarettes at the end of the session.

Table 2. Schedule of Events: Test Session*

Time point (min)	Measures and Events
Baseline	CO, urine and blood samples, HR/BP, M-NWSC, BQSU, SAFTEE, CPT
0	IV Infusion 1 (nicotine over 2.5 min or 5min) starts
1	HR, DEQ, plasma nicotine
3	HR, DEQ, plasma nicotine
5	HR, DEQ
6	plasma nicotine
8	HR, DEQ
10	IV Infusion 1 ends, HR, DEQ, BQSU,
12	plasma nicotine
13	HR, DEQ,
15	HR, DEQ, plasma nicotine
18	HR, DEQ
20	HR, DEQ, plasma nicotine
25	HR, DEQ,
30	HR/BP, DEQ, BQSU, CPT, M-NWSC, MCP
45	HR, DEQ, BQSU, M-NWSC CPT, plasma nicotine
60	IV Infusion 2 (Saline) starts
61	HR, DEQ, plasma nicotine
63	HR, DEQ, plasma nicotine

65	HR, DEQ
66	plasma nicotine
68	HR, DEQ
70	IV Infusion 2 ends, HR, DEQ, BQSU,
72	plasma nicotine
73	HR, DEQ,
75	HR, DEQ, plasma nicotine
78	HR, DEQ
80	HR, DEQ, plasma nicotine
85	HR, DEQ,
90	HR/BP, DEQ, BQSU, CPT, M-NWSC
105	HR, DEQ, BQSU, M-NWSC CPT, plasma nicotine
120	IV Infusion 3 (nicotine over 2.5 min or 5min) starts
121	HR, DEQ, plasma nicotine
123	HR, DEQ, plasma nicotine
125	HR, DEQ
126	plasma nicotine
128	HR, DEQ
130	IV Infusion 3 ends, HR, DEQ, BQSU,
132	plasma nicotine
133	HR, DEQ,
135	HR, DEQ, plasma nicotine
138	HR, DEQ
140	HR, DEQ, plasma nicotine
145	HR, DEQ,
150	HR/BP, DEQ, BQSU, CPT, M-NWSC
165	HR, DEQ, BQSU, M-NWSC CPT, plasma nicotine
180	End of session, HR/BP, DEQ, plasma nicotine, M-NWSC, BQSU, SAFTEE, MCP
190	Discharge

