repeated measures. Because of the potential skewed distributions of the subjective effects data, transformations will be applied as necessary. We will evaluate the main and interactive effects of cigarette assignment and delivery rate. We anticipate statistically significant main effects of cigarette assignment, nicotine delivery rate and a significant interaction between cigarette assignment and nicotine delivery rate. To better understand the dose effects of nicotine delivery rate and whether they are moderated by cigarette assignment, we will construct specific contrasts among the four doses to test whether there is an indication of significant linear, quadratic, linear on log-scale or sigmoidal dose-response relationships across, or within menthol-preference groups. The possible dose-response curves identified by the specific mean contrasts will be compared by fitting linear and non-linear (as necessary) dose-response models with continuous dose and selecting the best-fitting model by the Akaike's Information Criterion (AIC). To test for an effect of delivery rate on smoking urges, assessed by the BQSU (Factor 1 and 2) scores, we will use similar modeling approach described for subjective effects, but we will also include time as a within-subject factor with outcomes for minute 0, 10, 30, 60 and 120. We anticipate a significant main effect of menthol-preference, nicotine delivery rate and potentially a significant interaction between cigarette assignment and nicotine delivery rate.

Exploratory Aim#1: To explore the dose-effect curves of nicotine delivery rate for a) reinforcement (assessed with the Multiple-Choice Questionnaire), b) heart rate and blood pressure, and c) tobacco withdrawal severity, assessed with self-report symptoms and cognitive performance.

The primary outcome for the analysis of reinforcement will be the crossover point determined by the monetary choice procedure for the four infusion conditions. The crossover point is the monetary value at which a subject chooses money over receiving the infusion for that condition. It is a continuous measure (dollar amount) from -20 to +20 with values > \$0 indicating reinforcement. Tobacco withdrawal severity is measured by the MNWS and CPT taken at 0, 30, 60 and 120 min after the beginning of infusion. The models will be similar to the one described for Specific Aim #1 with time as an additional within-subject factor for heart rate, blood pressure and tobacco withdrawal severity.

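### Saline is always the second infusion, an hour after nicotine, so nicotine versus saline and any saline-anchored curve rest on an unstated assumption of no carry-over and no non-linear position effect

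*Combined protocol and SAP*

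**What the plan says.** Section 9.B (Drugs, Nicotine administration) gives three infusions per session: "The order of infusions will be: 1) 5-min or 2.5-min nicotine infusion, 2) saline infusion and 5-min or 2.5-min infusion". The reason offered is: "This infusion order was chosen to minimize carry over effects between nicotine infusions". The Overview of the study in Section 9.C repeats the order. The first infusion is nicotine at 1 mg/70 kg, and it is followed by "saline delivered over 10 minutes, and nicotine (1 mg/ 70kg to a maximum dose of 1 mg) delivered over 2.5 or 5 minutes". Table 2 starts nicotine at minutes 0 and 120, and its minute-60 entry reads "IV Infusion 2 (Saline) starts". There is one session per phase, with the same layout in both phases.

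The overview also says: "We propose a placebo-controlled study that will recruit male and female menthol nicotine dependent smokers". Section 12.3 describes the nicotine treatment as double-blind. On masking, Section 9.B says that participants do not know the randomization and adds: "Participants will be blind to the order of nicotine infusions". It does not say whether the fixed place of saline is concealed.

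In the statistical section, the Specific Aim #1 model takes peak change on each DEQ item as the response. Its fixed terms are cigarette assignment, phase, delivery condition and their interaction. There is no term for infusion position or carry-over, and the reference value for the change is not defined. The plan then builds contrasts among four doses to look for "linear, quadratic, linear on log-scale or sigmoidal dose-response relationships" and picks the best-fitting curve by AIC. Section 9.B provides only three conditions: saline, 5-minute nicotine and 2.5-minute nicotine.

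**The concern.** Saline never occupies position 1 or 3, so a model that sees only the delivery condition credits to saline everything that belongs to being second. By the time saline starts, Table 2 has recorded BQSU four times (baseline and minutes 10, 30 and 45) and CPT three times (baseline and minutes 30 and 45). All but the baseline readings follow the start of nicotine. The stated reason for the order recognises carry-over from one nicotine infusion to the next, but carry-over into saline is not discussed. The team's own preliminary study gave saline in random order.

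Two things are at stake. One is any statement that nicotine differs from saline on subjective effects, urges, withdrawal or CPT. The other is the lower end of the dose-effect curves: with only two nicotine rates, every quadratic or sigmoidal shape needs saline as its third point.

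**Working it through.** **Inputs.** Order and timing: Sections 9.B and 9.C and Table 2. Infusion rates: Section 9.B. Analysed number, 30: Rationale for sample size. Assumed, because the documents do not settle it: each session contains one fast (2.5-minute) and one slow (5-minute) nicotine infusion, with the two orders balanced; and a one-compartment half-life between 15 and 180 minutes.

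**1. The plan's own figures.** 0.096 × 150 s × 70 kg = 1,008 µg and 0.048 × 300 s × 70 kg = 1,008 µg. Both rates deliver about 1 mg/70 kg, as stated. The sample size also reproduces: 30/0.8 = 37.5, rounded up to 38. The point does not depend on either figure.

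**2. Aliasing.** In every session the saline indicator equals the position-2 indicator, so fast + slow = position 1 + position 3. With a three-level position factor the fixed effects have 6 columns and rank 5.

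**3. What can be estimated.** Standard errors are in units of the residual SD, for 30 people × 2 sessions = 60 sessions:
- Nicotine average minus saline: √((1/2 + 1)/60) = 0.158
- Fast minus slow: √(2/60) = 0.183
- Cigarette × (nicotine minus saline): √(2 × 1.5/30) = 0.316
- Cigarette × (fast minus slow): √(2 × 2/30) = 0.365

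| Contrast | No position term (as planned) | Position factor, same for both cigarettes | Position factor differing by cigarette |
|---|---|---|---|
| Nicotine − saline | 0.158 | not estimable | not estimable |
| Fast − slow | 0.183 | 0.183 | 0.183 |
| Cigarette × (nicotine − saline) | 0.316 | 0.316 | not estimable |
| Cigarette × (fast − slow) | 0.365 | 0.365 | 0.365 |

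For comparison, six balanced orders with saline in all three positions would give rank 6 of 6 and the same 0.158. This locates the cause in the fixed order. It does not recommend a different order, because whether nicotine infusions may follow one another directly is a clinical matter for the investigators.

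**4. Bias.** Let p1, p2 and p3 be the position effects, including carry-over. In the planned model the bias in nicotine minus saline is (p1 + p3)/2 − p2.
- Shift in position 2 only (0, 1, 0): 0 − 1 = −1.0
- Equal shift in positions 2 and 3 (0, 1, 1): 0.5 − 1 = −0.5
- Linear drift (0, 0.5, 1): 0.5 − 0.5 = 0

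The bias in cigarette × (nicotine minus saline) is this quantity under non-menthol minus the same quantity under menthol. It is zero when the position effects are common to both.

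**5. Residual from infusion 1.** The fraction left is 0.5^((t − infusion length)/half-life), with t in minutes. The two values in each range are for the fast and slow infusions.

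| Assumed half-life (min) | At minute 60 | At minute 120 |
|---|---|---|
| 15 | 7–8% | under 1% |
| 30 | 27–28% | 7% |
| 60 | 52–53% | 26–27% |
| 120 | 72–73% | 51–52% |
| 180 | 80–81% | 64% |

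A residual that decays is larger at position 2 than at position 3. It is therefore not a linear drift and does not cancel in step 4.

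**6. Curve shapes.** The available rates are 0, 0.048 and 0.096 µg/kg/s. Without the zero, two points remain and no curvature can be tested. On a log scale the zero also needs an offset, which the plan does not give.

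**The case against.** The strongest reply is that the main question is protected. Hypothesis 1 compares cigarette conditions, and saline is second in both phases, so a position effect common to both cancels from cigarette × (nicotine minus saline). Position 2 is also the midpoint, so roughly linear practice or fatigue cancels from nicotine minus saline itself. Both arguments stand. They are conditional, though. The plan's own Background reports that switching to non-menthol cigarettes was associated with faster nicotine metabolism, which is a reason to expect the residual at minute 60 to differ by cigarette. The documents do not quantify that difference.

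A second reply is that the primary outcome is a change, that plasma nicotine is measured, and that the nicotine metabolite ratio is a planned covariate. A change from a pre-infusion value would remove much of a residual level, but the reference is undefined. Table 2 lists no DEQ before infusion 1, and the last one before saline is at minute 45. Measured plasma nicotine replaces delivery condition only in Exploratory Aim #2.

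Three stronger readings are tempting, and the documents do not support them:
- **Saline cannot serve as a zero point at all.** It can, under the stated assumption.
- **Nicotine-minus-saline differences are biased towards zero.** The direction depends on the shape of the position effect and on the undefined reference value.
- **Participants know which infusion is saline.** A fixed place in two sessions makes guessing plausible, but all infusions last 10 minutes, blinding to the randomization is stated, and nothing shows what participants are told.

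Reinforcement is largely outside this point: Table 2 lists the MCP only at minutes 30 and 180, so none directly follows saline.

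**Conclusion.** The concern holds in a limited form. The confounding of saline with position 2 and with carry-over from infusion 1 is complete and follows from the text alone. Nicotine versus saline, and every curve shape that uses saline as zero, is identified only if there is no carry-over and no non-linear position effect. The plan neither states nor examines that assumption. Cigarette × (nicotine minus saline) further needs the carry-over to be the same under both cigarettes. Fast minus slow and cigarette × (fast minus slow) do not depend on saline and remain estimable, given one infusion of each rate per session and balanced orders.

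The size of any bias cannot be fixed from the documents. The 7% to 81% range is a share of infusion 1 under assumed half-lives, not an effect on any outcome.

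**What to change.** Leave the infusion order as it is and change the analysis plan and the wording:

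1. Base the delivery-rate and cigarette-by-rate conclusions on fast minus slow, with a term for infusion position (1 versus 3).
2. Keep saline as a position-2 reference. Label nicotine-versus-saline contrasts and saline-anchored shapes as conditional on no carry-over and no non-linear position effect.
3. Define change from the last value before each infusion. For the DEQ this needs a rating before infusion 1, which Table 2 does not list, or a stated convention.
4. Add a sensitivity analysis that adjusts for the last plasma nicotine before each infusion; for saline this is the 45-minute sample already collected. It addresses residual nicotine but not other position effects.
5. Draw no unqualified nicotine-versus-saline conclusion for urges, withdrawal or CPT.
6. Qualify the placebo-controlled description by stating that the position of saline is fixed.
7. Reconcile the four doses in the statistical section with the three conditions in Section 9.B.

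The direct cost is mainly SAP and protocol wording, but there is a scientific price. The zero end of the curve and the placebo comparison become conditional. Two rates alone cannot show a quadratic or sigmoidal shape, nor separate the leftward shift in Hypothesis 1 from a vertical one.

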*Saline infusions will follow each nicotine infusion to maintain a 10-min total infusion time for each test session. Abbreviations: CO: Alveolar carbon monoxide; HR/BP: Heart rate/Blood pressure; M-NWSC: Minnesota Nicotine Withdrawal Symptom Checklist; BQSU: Brief Questionnaire of Smoking Urges; CPT: Continuous Performance Test; DEQ: Drug Effects Questionnaire; SAFTEE: Systematic Assessment for Treatment Emergent Events. MCP: Money choice procedure.

7) Statistical analysis and sample size estimates

Specific Aim #1: To examine if switching from menthol to non-menthol cigarettes will change the dose-effect curves for positive subjective effects and alleviation of smoking urges as a function of nicotine delivery rate.

Positive subjective effects of nicotine will be assessed with the “Like the Drug Effects” and “Good Drug Effects” items from the DEQ, consistent with the FDA Guidance on abuse potential assessment (10). These items have been shown to correlate with the abuse potential of drugs of abuse. Effects will be tested using linear mixed effects models with peak change on each DEQ item as a response variable, cigarette-assignment (menthol vs. non-menthol), phase (1 vs.2) and nicotine delivery condition as within-subject factors and their interaction. Random effects for subject and condition within subject will be used to account for correlations between

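### Above about 70 kg the stated infusion rates, durations and 1 mg per-infusion maximum cannot all hold, and the dose variable for the curve fits is not defined as nominal or delivered

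*Combined protocol and SAP*

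**What the plan says.** The combined protocol and SAP describes the nicotine infusions in two places.

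- **B) Drugs, justification of doses and infusion rates.** The session total is given per body weight: "The total nicotine dose for each test session will be 2 mg/70 kg body weight". The limit and the rates follow: "For safety reasons, the maximum dose of nicotine for each infusion will be 1 mg. The infusion rates will be 0.096 and 0.048" µg/kg/s, for 2.5 and 5 minutes respectively.
- **C) Study procedures, Overview of the study.** The limit and rates are repeated, and each nicotine infusion is described as "nicotine (1 mg per 70 kg body weight to a maximum dose of 1 mg) delivered over 2.5 or 5 minutes".

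Three other passages bear on how this is to be read. Under Nicotine administration, "weight-adjusted nicotine and saline solutions will be prepared by the West Haven VA research pharmacy" on the morning of each session, and saline fills the rest of the 10 minutes after nicotine. Table 2 names the conditions by duration: "IV Infusion 1 (nicotine over 2.5 min or 5min) starts". The eligibility criteria (7. Subjects) contain no body-weight limit.

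In the statistical section, the Specific Aim #1 model has "nicotine delivery condition as within-subject factors and their interaction". A second step follows, introduced with "To better understand the dose effects of nicotine delivery rate". It uses contrasts and then compares fitted "dose-response models with continuous dose" by AIC. The section does not say whether that dose is the nominal or the delivered rate, or give its unit.

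**The concern.** A per-kg rate, a fixed duration and an absolute maximum agree only up to the weight at which their product reaches the maximum. Beyond it, at least one of the three must give way. The protocol gives the rates without a condition and does not say in words which one changes.

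Delivery rate is the x-axis of the trial's dose-effect curves, and the Significance section offers the results as benchmarks for nicotine delivery rates. If the published rates are not those that heavier participants received, the benchmark is mislabelled for them. If the x-variable for the curve fits is left open, nominal and delivered rate can give different curves, and the choice could be made after the data are seen.

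**Working it through.** **Inputs.** Rates 0.096 and 0.048 µg/kg/s, durations 2.5 min (150 s) and 5 min (300 s), maximum 1 mg (1000 µg) per infusion, dose 1 mg per 70 kg (B) Drugs; Overview of the study). The documents give no participant weights, so the weights below are illustrations.

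**1. Reproduce the stated rates.** (1000 µg / 70 kg) / 150 s = 0.0952 µg/kg/s, and (1000 / 70) / 300 = 0.0476. The stated figures are each 0.8% higher (0.096 / 0.0952 = 1.008), which is rounding. The rates are therefore those of 1 mg per 70 kg with no maximum applied.

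**2. Weight at which the maximum is reached.** 0.096 × 150 = 0.048 × 300 = 14.4 µg/kg, and 1000 / 14.4 = 69.4 kg. With the exact 1 mg per 70 kg it is 70 kg. The small difference is again rounding and is not part of the point.

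**3. Above that weight, w in kg.**
- Dose implied by stated rate and duration: 14.4 × w / 1000 mg.
- Maximum and durations kept: rate = 1000 / (150w) and 1000 / (300w) µg/kg/s. Shortfall from 1 mg/70 kg = 1 − 70/w.
- Maximum and rates kept: nicotine time = 1000 / (0.096w) and 1000 / (0.048w) s.
- Dose per kg at the maximum, either way: 1000 / w µg/kg.

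| Weight (kg) | Implied dose (mg) | Rates if durations kept (µg/kg/s) | Shortfall | Seconds if rates kept | Dose at maximum (µg/kg) |
|---|---|---|---|---|---|
| 80 | 1.15 | 0.083 / 0.042 | 12.5% | 130 / 260 | 12.5 |
| 90 | 1.30 | 0.074 / 0.037 | 22.2% | 116 / 231 | 11.1 |
| 100 | 1.44 | 0.067 / 0.033 | 30.0% | 104 / 208 | 10.0 |
| 120 | 1.73 | 0.056 / 0.028 | 41.7% | 87 / 174 | 8.3 |

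Up to 70 kg the dose is 1000 / 70 = 14.3 µg/kg.

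**4. Session total.** Taken alone, 2 mg per 70 kg gives 2 × 100 / 70 = 2.86 mg at 100 kg. Two infusions at the maximum give 2 mg.

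**5. Where it reaches the analysis.**
- *Condition as a factor.* In both readings each participant gets equal doses in the two nicotine conditions at a 2:1 rate ratio (for example 0.067 against 0.033). With stable weight over the study, the same holds under both cigarette assignments. The within-person contrasts stand.
- *Continuous dose.* If durations are kept, the two x-variables differ. At 120 kg the faster infusion runs at 0.056, which is 0.008 from the nominal slow rate (0.048) and 0.040 from the nominal fast rate (0.096). If rates are kept, nominal and delivered rate coincide and this problem does not arise.
- *Sex comparison.* Dose per kg falls with weight above 70 kg in either reading. This touches Exploratory Aim #3 only if weight differs by sex.

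**The case against.** The strongest reply is that the text is less open than the arithmetic suggests. The Overview attaches the durations to the dose after the maximum has been applied, Nicotine administration fixes the nicotine time and fills the remainder with saline, and Table 2 labels the conditions by duration. Weight-adjusted solutions also fit fixed pump times. On that reading the rates are simply nominal values that lack a qualifier. This largely stands: a reader might infer that the protocol is evenly split between changing the rate and changing the duration, and the wording does not support that. It remains an inference, because the same paragraph gives the per-kg rates with no exception. If the inference is right, the stated rates are incorrect for everyone above about 70 kg.

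A reader might also take the session total as a second, independent contradiction. It is not. The sentence directly after it limits each infusion, so read together the two infusions cannot exceed 2 mg. The total needs only the same qualifier.

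A further reply is that the curve fits are follow-up work, that continuous dose most naturally means the nominal condition value, and that Exploratory Aim #2 already models measured peak and AUC plasma nicotine. That limits the consequence, but the plasma models do not define the dose variable for Specific Aim #1.

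**Conclusion.** The conflict is real and rests on arithmetic alone: above about 70 kg the stated rates, durations and maximum cannot all hold. If the maximum and durations are kept, delivered rates are 12.5% below 1 mg/70 kg at 80 kg, 30% below at 100 kg and 42% below at 120 kg.

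The consequences are limited. The reported delivery rates and the continuous-dose and AIC fits are affected if durations are kept. The exploratory sex comparison is affected only on the assumption that weight differs by sex, which the documents neither state nor allow one to check. The share of participants above 70 kg is unknown for the same reason.

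A reader might infer that the menthol comparison, or the main test of delivery condition, is biased. The documents do not support that: condition enters as a within-subject factor, and with stable weight each person keeps the same dose and the same 2:1 rate ratio under both cigarette assignments. Severity is minor to moderate, with high confidence in the arithmetic and less in the size of the effect on the curve fits.

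**What to change.** 1. In B) Drugs and in the Overview of the study, reconcile rate, duration, session total and per-infusion maximum so that they agree at every body weight. Which of them governs is for the investigators.
2. Report the rates actually delivered.
3. Under Specific Aim #1, state before analysis whether continuous dose is the nominal or the delivered rate, with its unit. Run the other as a sensitivity analysis. Note there that delivered rate carries between-person weight differences that were not randomised.
4. Keep the body weight used to prepare the solutions, and the dose administered, as study data.
5. Optionally, add that weight as a sensitivity covariate in the Exploratory Aim #3 models for the main outcomes (the two DEQ items and the two BQSU factors).

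The cost is wording in three places and one additional set of curve fits. A weight must already be in hand to prepare weight-adjusted solutions. Table 2 does not list a weight at each session, however, so item 4 asks for the weight used in preparation and not for a new session measurement. The optional item costs a few extra models, each with one more parameter, at a planned size of about 30 to 38. Exploratory Aim #3 adds sex to every model, so confining the covariate to the main outcomes keeps that burden small.
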